²All “prior to drug administration” samples should be collected after at least 8 hours of fasting (the patient must not eat or drink anything but water).

³All “after drug administration” samples should be collected after patients are dosed with CB-839 HCl immediately after a meal.

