5.4.5.2 Collection of Blood in EDTA Tube for Plasma Processing

1. Label EDTA tube(s) according to the instructions in section 5.3.1.
2. Collect 10 mL of whole blood in EDTA (purple top) tube(s). After collection, keep blood at 4°C and process immediately (within 30-60 minutes of collection).
3. Process plasma by centrifuging for 10 minutes at 1,200 x g at room temperature.
4. **Using a clean transfer pipette**, transfer 1 mL of plasma into each of the labeled cryovials (using the label printed from the ETCTN Specimen Tracking System or following the instructions in section 5.3.1). Avoid picking up the blood cells when aliquoting by keeping the pipet above the cell layers and leaving a small amount of plasma in the tube. Tightly secure the cap of the vials before storage. Document the

time the plasma is processed.

5. Store plasma cryovials upright in a specimen box or rack in an -70°C to -90°C or colder freezer prior to delivering to laboratory. Do not allow specimens to thaw after freezing. Document the time the plasma is frozen.
6. Record the time the sample was processed to plasma and when the plasma is stored at -80°C.

5.4.5.3 Collection of Blood in EDTA Tube for PK Plasma Processing for Mayo Clinic

1. All “prior to drug administration” samples should be collected after at least 8 hours of fasting. Instruct patients to bring dose to the clinic and take dose (with food) after the baseline PK sample has been obtained on the days where PK sampling will occur.
2. Label both 3 mL EDTA (purple top) tubes for Telaglenastat (CB-839) HCl samples.
3. Collect blood in pre-labeled tube and gently invert tube to mix. Place on wet ice (or store at 4°C) until processing.
4. Blood must be processed for plasma isolation within 20 minutes of collection. The time at which the sample was collected from the patient and the time at which the plasma was stored in an aliquot at -80°C must be recorded in the Specimen Tracking System for every sample to ensure adequate handling.
5. Centrifuge blood at 1,000 – 1,300 x g (relative centrifugal force [RCF]) for 10 minutes in a refrigerated centrifuge kept at 4°C.
6. Following centrifugation, remove the plasma (top yellowish or clearish layer) and create aliquots in equal volumes of at least 0.5 mL in labeled 2 mL screw-top cryovials. Refer to Section 5.4.1.2 for labeling instructions.

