5.4.5.4 Collection of Blood in EDTA Tube for Oncometabolite Analysis

1. All “prior to drug administration” samples should be collected after at least 8 hours of fasting. Instruct patients to bring dose to the clinic and take dose (with food) after the baseline oncometabolite sample has been obtained on the days where oncometabolite sampling will occur.
2. Label both 3 mL EDTA (purple top) tubes for Telaglenastat (CB-839) HCl samples.
3. Collect blood in pre-labeled tube and gently invert tube to mix. Place on wet ice (or store at 4°C) until processing.
4. The peripheral blood sample must be centrifuged within 30 to 60 minutes of collection at 4°C with a centrifuge speed of 2000 x g for 15 minutes.
5. After centrifugation, remove plasma (top yellowish or clearish layer) and create 0.5 mL aliquots in labeled 2 mL screw-top cryovials.
6. Immediately freeze the aliquots upright in a -70 to -80°C freezer until shipment to the EET Biobank according to the instructions below. The time at which the sample

was collected from the patient and the time at which the plasma was stored in an aliquot at -80°C must be recorded in the Specimen Tracking System for every sample to ensure adequate handling.

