6. TREATMENT PLAN

6.1 Agent Administration

Treatment will be administered on an outpatient basis. Reported adverse events and potential risks are described in Section 10. Appropriate dose modifications are described in Section 7. No investigational or commercial agents or therapies other than those described below may be administered with the intent to treat the patient's malignancy.

This phase 2 basket clinical trial utilizes single agent CB 839 HCl at the recommended phase 2 dose at 800 mg (Table 2 and 3).

Table 2. Treatment Plan for Telaglenastat (CB-839) HCl as a single agent	
Category	Treatment Plan
Telaglenastat (CB-839) HCl agent dose	800 mg
Telaglenastat (CB-839) HCl administration and schedule	Telaglenastat (CB-839) HCl dose by mouth twice daily, approximately 12 hours apart, immediately after a meal on day 1 to day 28, repeated every 28 days
Duration of treatment	Repeated every 28 days until unacceptable toxicity or disease progression. Refer to Section 6.3 for additional stopping criteria.
Duration of the study	Upon completion of follow-up procedures.
Duration of follow-up	Every 3 months (\pm) 14 days after the last administered treatment dose

If patient develop toxicity then the dose can be reduced as per Table 3.

Table 3. Dose Reductions of Telaglenastat (CB-839) HCl	
Dose Level	Telaglenastat (CB-839) - HCl Dose

Starting dose	800 mg BID
First dose reduction	600 mg BID
Second dose reduction	400 mg BID
Third dose reduction	Discontinue Telaglenastat (CB-839) HCl

The patient will be requested to maintain a medication diary of each dose of medication. The medication diary will be returned to clinic staff at each clinic visit.

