Storage: Store at room temperature (20°C-25°C). Excursions +/- 5°C are permitted. If a storage temperature excursion is identified, promptly return Telaglenastat (CB-839) HCl to (20°C-25°C) and quarantine the supplies. Provide a detailed report of the excursion (including documentation of temperature monitoring and duration of the excursion) to [contact] for determination of suitability.

Stability: Stability studies are ongoing.

Route of Administration: Oral, approximately 12 hours apart, with food. Administer the first dose immediately after breakfast, the second dose approximately 12 hours later. Doses should be taken at approximately the same times each day. Missed doses may be taken if it is not more than three hours past the scheduled administration time for the missed dose. Vomited doses should not be made up.

Metabolism: In *in vitro* studies, Telaglenastat (CB-839) HCl is metabolized by amide hydrolysis and to a lesser extent, P450-mediated hydroxylation.

Potential Drug Interactions: In *in vitro* data, Telaglenastat (CB-839) HCl is a weak *o* inhibitor of CYP2C9; therefore, concomitant medications that are metabolized by CYP2C9 should either be given with caution (including closely monitoring for signs of toxicity or altered efficacy) or substituted with a non-CYP2C9 substrate. Telaglenastat (CB-839) HCl is not an inhibitor of CYP1A2, CYP2B6, CYP2C8, CYP2C19, CYP2D6, and CYP3A4 nor an inducer of CYP1A2, CYP2B6, and CYP3A4.

Telaglenastat (CB-839) HCl requires low pH conditions for optimal solubilization. Concomitant use of proton pump inhibitors (PPIs) should be avoided due to significantly reduced exposure to Telaglenastat (CB-839) HCl. Patients may be switched to shorter acting agents such as histamine H₂ receptor antagonists (H₂RA) and as-needed antacid buffering agents (e.g. calcium carbonate, magnesium hydroxide and aluminum hydroxide) since, based on limited clinical data, they do not appear to result in a significant reduction of Telaglenastat (CB-839) HCl exposure. It is recommended that Telaglenastat (CB-839) HCl be dosed at least 2 hours before or at least 2 hours after antacid therapy.

Patient Care Implications: Women of child-bearing potential must have a negative pregnancy test prior to starting Telaglenastat (CB-839) HCl and use two forms of effective birth control while receiving Telaglenastat (CB-839) HCl.

Availability

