7. Radiologic evaluation (CT or MRI or PET-CT) will be performed at screening within 28 days prior to C1D1, every 2 cycles (8 weeks), ± 7 days, for the first 13 cycles, then every 3 cycles (12 weeks) ± 7 days and EOT.
8. Tumor measurement: Per RECIST v1.1 for solid tumors and per Modified RECIST (Byrne and Nowak 2004) for pleural mesothelioma. Tumor measurements are repeated every 2 cycles (every 8 weeks) ± 7 days, for the first 13 cycles, then every 3 cycles (12 weeks) ± 7 days and EOT. Documentation (radiologic) must be provided for patients removed from study for progressive disease.
9. Tumor-specific markers, such as CA19-9, CA-125, CEA, PSA, etc. will be tested at the time with radiologic evaluation.
10. Whole blood sample for oncometabolomics and pharmacokinetics will be collected on Day 1 and Day 15 prior to drug administration and after drug administration at 0.5, 1, 2, 4, and 8 hours. In addition, oncometabolomics will be collected on Week 4 (C1D22) post Telaglenastat (CB-839) HCl dose. All "prior to drug administration" samples should be collected after at least 8 hours of fasting (the patient must not eat or drink anything but water). All "after drug administration" samples should be collected after patients are dosed with Telaglenastat (CB-839) HCl immediately after a meal.
11. Optional whole blood sample for exploratory genetic and biomarker testing for cfDNA and WES/RNASeq will be collected at screening, at C1D22, C2D22 and disease progression (EOT) for patients who are consented for such analysis under fasting conditions.
12. Tumor Biopsy: Tumor biopsy at screening are required for all patients for exploratory analyses. In addition, archival tissue samples will be collected if available. Optional on-treatment biopsy will be collected on week 4 (C1D22 ± 3 days) and upon disease progression at EOT. Coagulation tests must be performed and evaluated prior to all biopsy procedures. Patients are consented for tumor biopsy.
13. Telaglenastat (CB-839) HCl dose by mouth twice daily, immediately after a meal on continuous dose from day 1 to day 28-day cycle.
Dosing may occur prior to, during, or after the clinic visit, according to the patient's usual administration schedule.
14. For patients with $\geq SD$ for at least 13 cycles who are on a steady dose for ≥ 2 cycles, study assessments may be reduced to every 3 cycles (i.e., at Cycles 16, 19, 22, etc.) and 3 cycles worth of study medication can be provided at clinic visits.

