APPENDIX G MEDICATION DIARY

Study Name: A Phase II Basket Trial of Glutaminase Inhibitor (BeGIN) Telaglenastat (CB-839) HCl in Patients with NF1 Aberrations, NF1 Mutant Malignant Peripheral Nerve Sheath Tumors (MPNST), KEAP1/NRF2 and LKB1 Aberrant Tumors

CTEP Study ID: 10220

Patient Initials: _____

Patient Identification Number: _____

Instructions to the patient:

PLEASE complete and return this dosing diary along with any unused Telaglenastat (CB-839) HCl and the container(s). You will receive a new dosing diary for each treatment cycle. Thank you for your participation in the very important study!

You will take: Telaglenastat (CB-839) HCl

Each time you take the Telaglenastat (CB-839) HCl study medication, your dose is 800 mg and is made up of four 200 mg tablets.

How to store your Telaglenastat (CB-839) HCl study medication

The Telaglenastat (CB-839) HCl study medication must be stored at room temperature (below 30°C/86°F) at all times. Please read the medication label for additional storage instructions.

How to take your Telaglenastat (CB-839) HCl study medication

- The Telaglenastat (CB-839) HCl study medication is to be taken twice daily for 28 days (1 cycle is 28 days).
- Each dose is taken orally (by mouth) with food around the same time each morning or evening. Administer the first dose immediately after breakfast, the second dose approximately 12 hours later.
 - Please note that on Cycle 1 Days 1 and 15, your morning dose of Telaglenastat (CB-839) HCl will be taken while fasting (at least 8 hours without eating or drinking anything but water).

If you miss the daily dose according to the schedule,

- The dose should be taken as soon as possible, but not more than 3 hours after the missed dose was scheduled.
- Vomited doses should not be made up.

How to complete your Telaglenastat (CB-839) HCl dosing diary

It is very important that you complete this dosing diary as accurately as possible and bring it

completed along with all remaining study medication (used and unused containers) to your next clinic visit.

Please fill-in this dosing diary each day that you are scheduled to take study medication. Write the date in the box marked Date. Please record the exact time you took your study medication and how many tablets taken.

It is important that you do not miss any of your study medication, but if you do please provide a reason in the “Comments” box along with any other comments you would like the doctor to know.

Cycle number: _____

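### The patient diary has the Cycle 1 Day 1 and Day 15 morning doses taken fasting, while the rest of the protocol requires them with or right after a meal

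*Combined protocol and SAP*

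**What the plan says.** Appendix G first gives a general rule that doses are taken with food. Under that rule, as a sub-bullet for Cycle 1 Days 1 and 15, it adds: "your morning dose of Telaglenastat (CB-839) HCl will be taken while fasting (at least 8 hours without eating or drinking anything but water".

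The rest of the protocol contains no such exception:

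- Section 6.1, Table 2: the dose is taken "immediately after a meal on day 1 to day 28, repeated every 28 days".
- Section 6.1.1: the drug is taken at breakfast and dinner.
- Section 8.1.1, Route of Administration: "Administer the first dose immediately after breakfast, the second dose approximately 12 hours later".
- Section 5.1, footnote 3, on post-dose samples: "samples should be collected after patients are dosed with CB-839 HCl immediately after a meal".
- Section 5.4.5.3 (PK plasma): patients bring the dose to clinic and "take dose (with food) after the baseline PK sample has been obtained on the days where PK sampling will occur".
- Section 5.4.5.4 (oncometabolites): "take dose (with food) after the baseline oncometabolite sample has been obtained on the days where oncometabolite sampling will occur".
- Section 11, calendar footnote 10, on post-dose samples: "samples should be collected after patients are dosed with Telaglenastat (CB-839) HCl immediately after a meal".

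The fasting requirement in sections 5.1, 5.4.5.3, 5.4.5.4 and 11 applies to the sample drawn before dosing. The specimen table in 5.1 marks only the 0-hour draw as fasting.

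**The concern.** The diary is the instruction the patient holds. Because the fasting line sits beneath the with-food rule, it reads as a deliberate exception for those two days. What it describes as fasting is the dose itself; it mentions neither a blood draw nor a meal between draw and dose.

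Two things are at stake.

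- **Treatment.** A patient who complies is dosed contrary to Table 2, in the state that section 6.1.1 associates with lower absorption and more elevated liver function tests.
- **PK and PD data.** Days 1 and 15 are the only serial sampling days, and section 5.7 lists both assays as mandatory and integrated. Section 9.3 plans to test pharmacodynamic change between 0 and 8 hours and to relate it to response. Under the body of the protocol that contrast is fasting pre-dose against fed post-dose; under the diary it is fasting throughout. A mixture of the two would be hard to interpret unless meal status were known. Section 2.2.4 itself attributes part of the observed PK variability to food intake.

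Meal status may not be recoverable. The diary has dose time, tablet count and free-text comments but no meal field, and the blood label items in 5.3.1.1 do not include it. Section 5.4.5.3 also refers to nurse's notes, a flow sheet and a pharmacology reporting form. Those forms are not shown.

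**Working it through.** The plan states no figure to reproduce. The check is a comparison of instructions, followed by simple arithmetic on how far the conflict reaches.

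**Side by side, Cycle 1 Days 1 and 15**

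| Item | Appendix G | Sections 5.1, 5.4.5.3, 5.4.5.4, 6.1, 8.1.1, 11 |
|---|---|---|
| Pre-dose draw | not mentioned | fasting, at least 8 hours |
| Morning dose | fasting, at least 8 hours | with or right after a meal |
| Post-dose draws | would follow a fasted dose | follow a fed dose |

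The pre-dose draw is fasting under both texts. The dose and every post-dose draw are in conflict. The likely cause is that the fasting rule for the draw was carried over to the dose.

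**Reach of the conflict**

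- Serial draws, per assay and patient: 6 time points × 2 days = 12, of which 5 × 2 = 10 are post-dose (0.5, 1, 2, 4 and 8 hours). The single Week 4 post-dose oncometabolite draw is outside this count.
- Full cohort of 27, all sampled: 10 × 27 = 270 post-dose draws per assay.
- Doses: 2 / (28 × 2) = 2/56 = 3.6% of Cycle 1 doses.

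These counts show what the conflicting text covers. They do not measure bias.

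**Possible PK effect**

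- Input: the 1.3-fold higher AUC0-8 with food on Cycle 1 Day 1 (section 2.2.4; section 6.1.1 gives about the same figure).
- Fasted relative to fed: 1 − 1/1.3 = 23.1% lower.
- If a share *f* of patients takes the dose fasted, the mean falls by *f* × 23.1%. The documents give no value for *f*, so these are assumptions:

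| Assumed *f* | Reduction in mean AUC0-8 |
|---|---|
| 10% | 2.3% |
| 25% | 5.8% |
| 50% | 11.5% |

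- For scale, SD/mean of AUC0-8 from Table 1 (section 2.3): 5.8/7.9 = 73% at 600 mg BID (n = 48) and 4.7/5.0 = 94% at 800–1000 mg BID (n = 5).

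The shifts are small against that spread. The 1.3-fold input is also weak: section 2.2.4 calls it non-significant, and it compares a fasted three-times-daily group with a fed twice-daily group. The documents give no meal effect for glutamine, glutamate or aspartate and state no PK analysis, so the effect on the section 9.3 comparison cannot be put into numbers.

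**The case against.** The strongest reply is that site procedure largely controls these two doses. Sections 5.4.5.3 and 5.4.5.4 have the patient bring the dose to clinic and take it with food once the baseline sample is drawn, and staff must know the dose time to schedule the later draws. On that view the diary mainly ensures that the patient arrives fasting, which is what the protocol wants, and what remains is a minor wording slip in an appendix.

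Much of this stands. Mixed fed and fasted dosing is possible but not certain. Calendar footnote 13 says "Dosing may occur prior to, during, or after the clinic visit", but it is a general rule; the sampling-day sections are more specific, and a patient who dosed at home would also lose the pre-dose sample, which would be noticed. The more realistic risk is a patient in clinic who declines food because of the diary and is not corrected. Nothing in the documents addresses the liver risk of two isolated fasted doses, which is probably small. Meal status would not ordinarily be expected on a tube label, and with the PK forms unseen no recording gap is proven.

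None of this reconciles the texts. The arrive-fasting-then-eat reading is probably what was intended, but it is not what the patient is told, and correct dosing then depends on staff overriding a written instruction.

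**Conclusion.** The concern holds. Appendix G contradicts the treatment plan and all the sampling instructions for the Cycle 1 Day 1 and Day 15 morning doses, and nothing elsewhere in the documents supports the exception. It should be corrected. Confidence is high in the textual conflict and low in the size of any effect: the AUC range above rests on an assumed share of fasted patients and on a non-significant, confounded food effect. The consequence is confined to two doses and the data drawn after them. The response endpoint, the two-stage rule and the stated power do not depend on it.

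**What to change.** Replace the diary sub-bullet with wording such as: *On Cycle 1 Days 1 and 15, have only water for at least 8 hours before your first blood draw. After that draw, eat a meal and take your dose as soon as you finish it.*

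On those two days, also record meal time or fed/fasted status next to the dose time, so that the condition of each profile is known. This second item is useful but secondary to the wording change.

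The cost is one diary edit and one recorded item on two days. No samples are added, and neither the design nor section 9.3 changes. For patients already past Cycle 1 Day 15 the edit comes too late; sites can check whether their existing records show meal status.
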